4. ANALYSIS SETS

Data for all subjects will be assessed to determine if subjects meet the criteria for inclusion in each analysis population prior to unblinding and releasing the database and classifications will be documented per standard operating procedures.

4.1. Full Analysis Set

The primary analysis population will be the Full Analysis Set (FAS) defined as all subjects who are randomized into the study and receive at least 1 dose of investigational product.

4.2. Per Protocol Analysis Set

No per protocol analysis set will be defined.

4.3. Safety Analysis Set

The safety analysis set will be defined as all subjects who receive at least 1 dose of investigational product.

A randomized but not treated subject will be excluded from the safety analysis set. A treated but not randomized subject will be included in the safety analyses.

4.4. Other Analysis Sets

No other analysis sets will be used.

5. GENERAL METHODOLOGY AND CONVENTIONS

The primary analysis will be performed to assess efficacy and safety when all subjects enrolled complete their Month 6 study visit (or drop out before Month 6 visit) and data are cleaned and locked. However, the final analyses will be performed after all subjects complete the study.

5.1. Hypotheses and Decision Rules

No formal hypotheses are to be tested.

5.2. General Methods

For the primary objective, analyses will be performed for comparisons of the following two dose groups:

- Tofacitinib 10 mg BID dose group: subjects who are initially assigned to tofacitinib 10 mg BID at randomization
- Tofacitinib 5 mg BID dose group: subjects who are initially assigned to tofacitinib 5 mg BID at randomization, regardless of whether the dose is escalated back to tofacitinib 10 mg BID or not (Data collected after the dose escalation from tofacitinib 5 mg BID to 10 mg BID will not be included in the analyses.)

For the first secondary objective, analyses will be performed for comparisons of the following two regimen groups:

- Tofacitinib 10 mg BID regimen group: subjects who are initially assigned to tofacitinib 10 mg BID at randomization.
- Tofacitinib 5 mg BID regimen group: subjects who are initially assigned to tofacitinib 5 mg BID at randomization, staying on tofacitinib 5 mg BID or having dose escalation from tofacitinib 5 mg BID to 10 mg BID. Data collected after the dose escalation will be included in the analyses.

For the second secondary objective, summary descriptive statistics will be reported for the subgroup of subjects who are initially assigned to tofacitinib 5 mg BID and later are re-treated with tofacitinib 10 mg BID based on the observed case data using the original windowing rules. In addition, the efficacy data after the dose escalation will be summarized using the new windowing rule by resetting the baseline (Day 0) at the dose escalation time.

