1. The baseline visit of Study A3921288 is the same visit as the last visit in Study A3921139. All procedures done at the last visit in A3921139 for subjects enrolled into Study A3921288 will be used as the baseline data for Study A3921288. Procedures listed as OLE procedures will NOT BE REPEATED at baseline of Study A3921288. Only those procedures marked with an 'X' will be performed at the baseline visit of Study A3921288.
2. Medical history from Study A3921139, including resolved adverse events (AEs) will be used for Study A3921288. Ongoing AEs from Study A3921139 will be followed throughout Study A3921288.
3. The targeted physical examination consists of weight, general appearance, and examinations of eyes, mouth, lungs, heart, abdomen, musculoskeletal, extremities, skin and lymph nodes.
4. Urine β -hCG to be performed only for females of childbearing potential. Pregnancy testing may be performed more frequently per local regulations.
5. Stool samples will be collected at baseline and at each scheduled study visit to measure fecal calprotectin (see [Section 7.3.3.1](#)). In addition, stool samples should be obtained at the time of worsening disease and/or flare when possible.

6. Tuberculosis (TB) screening will be conducted at Month 12 using Quantiferon-TB[®] Gold Plus test (QFT) only for subjects in those countries in which TB prevalence has been reported at a rate of >50 cases per 100,000 persons (see [Section 7.3.3.2](#)). All subjects with positive results must have chest radiograph performed. Note: QFT should not be performed in subjects who had positive result during prior testing (screening visit in Induction Study A3921094 or A3921095 or prior annual visits in Study A3921139) and/or previously received adequate treatment for TB.
7. Safety monitoring for a subset of subjects in Japan only. See [Appendix 4](#) for details.
8. Flexible sigmoidoscopy/colonoscopy (if preferred) will be performed at Month 6, Month 18 and at ET for all subjects. In order for a subject to be eligible for Study A3921288, they must have an endoscopy performed in Study A3921139 ≤6 months prior to baseline of Study A3921288 with an endoscopic subscore of 0 or 1. Mayo endoscopic subscore will only be assessed by local site read.

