- Flexible sigmoidoscopy/colonoscopy (if preferred) will be performed at Month 30, Month 42 and at ET for all subjects. Mayo endoscopic subscore will only be assessed by local site read.
- Bowel movement (BM) diary data will be collected through a phone-based interactive voice recording system (IVRS) tool. Subjects will be instructed in its use at the Baseline visit. Subjects should start completing the BM diary daily approximately 7 days prior to their next scheduled visit. Study site staff should contact the subjects 7 days prior to the scheduled visit to ensure compliance. In addition, subjects should be instructed to start completing the BM diary whenever he/she experiences any worsening of UC symptoms anytime during the study.
- Per Amendment 2, all subjects will be asked at every study visit if they have any newly-developed risk factors for pulmonary embolism as described in [Section 7.3.6](#). At the time of Amendment 2, 138 subjects have been enrolled in the study and have each completed various durations of participation. Per Amendment 3, all subjects will be asked at each applicable visit if they have any newly developed risk factors for venous thromboembolism as described in [Section 7.3.6](#). At the time of Amendment 3, all subjects were enrolled and completed the Month 6 study visit. Therefore, this procedure will only be collected at visits applicable to each subject’s individual participation. If a subject has a newly identified risk factor for venous thromboembolism, the subject’s tofacitinib dose will be adjusted to open-label 5 mg BID.**

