If during the course of the study, a subject experiences an increase in clinical symptoms, such as an increase in rectal bleeding or an increase in stool frequency, then an endoscopy should be performed to assess if the subject is experiencing flare. Flare must be confirmed prior to performing any dose adjustments. In addition, subjects who experience atypical symptoms or features of their usual UC disease course or have significantly worsening disease activity assessments from the previous visit, or have the presence of risk factors such as recent antibiotic use or a recent history of *C. difficile* infection should have *Clostridium difficile* (*C. difficile*) toxin testing performed before assessing for flare and performing any dose adjustments.

Please refer to [Section 5.11](#) for tofacitinib dose adjustment guidelines and definition of flare.

Amendment 2

On 17 May 2019, the European Medicines Agency's (EMA) Pharmacovigilance Risk Assessment Committee (PRAC) issued interim recommendations on the restrictions for prescriptions of tofacitinib. These interim recommendations on the restrictions for prescriptions of tofacitinib state that patients who are at high risk of blood clots in the lungs must not be started on tofacitinib 10 mg BID, and that such patients currently taking tofacitinib 10 mg BID for any condition must be switched to alternative treatments. Updated guidance from PRAC will be provided to patients and their healthcare professionals in the European Union (EU) once PRAC has completed its review of all available data.

In light of the PRAC interim recommendations in the EU, Study A3921288 will be modified globally through protocol Amendment 2, which will involve the following updates:

1. The study investigator or designee will need to review each subject's medical history and study records, including their concomitant medications, to determine whether he/she is at high risk for developing pulmonary embolism. If he/she has any of the risk factors listed below, the subject's tofacitinib dose should be adjusted to open-label 5 mg BID (see [Section 5.11](#)).

A subject may be at high risk for pulmonary embolism if he/she:

- has heart failure;
- has inherited coagulation disorders;
- has had venous thromboembolism, either deep venous thrombosis or pulmonary embolism;
- is taking combined hormonal contraceptives or hormone replacement therapy;
- has malignancy (association is strongest with cancers other than non-melanoma skin cancers);

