7.2.3. Mayo Score

The Mayo score is an instrument designed to measure disease activity of UC. Mayo score ranges from 0 to 12 points. It consists of 4 subscores, each graded from 0 to 3 with higher scores indicating more severe disease (see [Appendix 2](#)).

- stool frequency (0-3).
- rectal bleeding (0-3).
- findings of flexible sigmoidoscopy (0-3).
- physician global assessment (PGA) (0-3).

Mayo score is assessed at Baseline, Month 6, Month 18, Month 30 and at Month 42/ET visits per the [Schedule of Activities](#).

The endoscopic findings will be locally read by study site investigator. The Mayo score will be calculated based on the subject's BM diary data (see [Section 7.2.1](#)) recorded over the 3 prior consecutive days.

The mucosal appearance of the sigmoidoscopic portion of endoscopic examination will be assessed for the Mayo endoscopic subscore, based on the definition provided in the protocol (see [Appendix 2](#)).

The PGA acknowledges the three other criteria, the patient's recollection of abdominal discomfort and general sense of wellbeing, and other observations, such as physical findings and the patient's performance status. The endoscopic subscore and the PGA should be

performed by a physician qualified to perform endoscopy, and it is recommended that the same physician performs all such assessments for a particular subject throughout the study, when possible.

Endpoints based on total Mayo score are defined below:

- Remission: total Mayo score of 2 points or lower, with no individual subscore exceeding 1 point and a rectal bleeding subscore of 0.
- Clinical response: decrease from baseline in total Mayo score of the Induction study, of at least 3 points and at least 30%, with an accompanying decrease in the subscore for rectal bleeding of at least 1 point, or absolute subscore for rectal bleeding of 0 or 1.
- Mucosal healing: an endoscopic subscore of 0 or 1.

Modified Mayo score consists of stool frequency subscore, rectal bleeding subscore and endoscopic subscore (ie, total Mayo score without PGA).

Endpoints based on modified Mayo score are defined below:

- Remission: an endoscopic subscore of 0 or 1, stool frequency subscore of 0 or 1, and rectal bleeding subscore of 0.

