9. APPENDICES

Appendix 1. Definition of Analysis Visit Windows

Analysis visit windows will be used for efficacy and safety data that are summarized by visit.

Visit Label	Target Day	Analysis Visit window
Baseline	Day 1 (First dose date)	Up to Day 1
Month 1	Day 30	Days 2-60
Month 3	Day 90	Days 61-135
Month 6	Day 180	Days 136-225
Month 9	Day 270	Days 226-315
Month 12	Day 360	Days 316-405
Month 15	Day 450	Days 406-495
Month 18	Day 540	Days 496—585
Month 21	Day 630	Days 586-675
Month 24	Day 720	Days 676-765
Month 27	Day 810	Days 766-855
Month 30	Day 900	Days 856-945
Month 33	Day 990	Days 946-1035
Month 36	Day 1080	Days 1036-1125
Month 39	Day 1170	Days 1126-1215
Month 42	Day 1260	After Day 1216
Follow-up		Follow-up visit and >last dose day+5

For time to event variables, there is no need to have the windowing. The actual days will be used as the event time or censored time. But the event rate at each visit will be estimated at the corresponding protocol schedule day +10 days using the Kaplan-Meier method. If more than one observation from the same subject falls into the same window, the value closest to the target day will be used as the observation for that analysis visit. All observations will, however, be included in the listings.

Analysis visit window Follow-up is defined by the visit name=FOLLOW_UP and >last dose day +5. For example, if a subject had the last dose on Day 1000 and the follow-up visit at Day 1006, then the data from Day 1006 will be treated as follow-up data instead of Month 33 data. However, if a subject had the last dose on Day 1000 and the follow-up visit at Day 1003, then the data from Day 1003 will be treated as Month 33 data.

New windowing rule for retreatment group:

Visit Label	Target Day	Analysis visit window
Baseline	Day 1 (dose escalation day)	Last observation up to Day 1 (dose escalation day)
Month 3	Day 90	Days 2-135
Month 6	Day 180	Days 136-225
Month 9	Day 270	Days 226-315
Month 12	Day 360	Days 316-405
Month 15	Day 450	Days 406-495
Month 18	Day 540	Days 496-585
Month 21	Day 630	Days 586-675
Month 24	Day 720	Days 676-765

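### After re-treatment with 10 mg BID, endpoints that need endoscopy are read in 3-monthly windows while scheduled endoscopy is yearly, so who is counted depends on how the subject is doing

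*SAP*

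**What the plan says.** The second secondary objective is the efficacy and safety of re-treatment in subjects who flare on 5 mg BID. SAP 5.2 plans two descriptive efficacy summaries for this subgroup. One is "based on the observed case data using the original windowing rules". For the other, "the efficacy data after the dose escalation will be summarized using the new windowing rule by resetting the baseline (Day 0") at the time of escalation. Appendix 1 lists the reset windows: Month 3 is Days 2-135, and Months 6 to 24 are 90 days each, ending at Day 765. If several observations share a window, "the value closest to the target day will be used as the observation for that analysis visit".

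The endoscopy calendar does not move with escalation. Protocol 7.2.3 states: "Mayo score is assessed at Baseline, Month 6, Month 18, Month 30 and at Month 42/ET visits". The Schedule of Activities footnotes say that endoscopy "will be performed at Month 6, Month 18 and at ET for all subjects" and, for the second part of the study, "will be performed at Month 30, Month 42 and at ET for all subjects". If symptoms increase, "then an endoscopy should be performed to assess if the subject is experiencing flare" (Protocol 3); subjects who have already escalated are not exempted.

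SAP 5.3.1 does not impute missing data for this subgroup. Subjects who start a new UC therapy other than oral 5-ASA or sulfasalazine are withdrawn (Protocol 5.10 and 6.4).

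**The concern.** Four endpoints need an endoscopic subscore: modified Mayo remission, total Mayo remission, mucosal healing and clinical response. In a reset window without a scheduled endoscopy, a subject who is doing well has no score and leaves the proportion. A subject who is doing badly may be scoped for symptoms or at ET and is counted. The rule of taking the value closest to target ignores why the endoscopy was done. Subjects who fail and are withdrawn then disappear from every later window. Whether a subject is in the denominator therefore depends on the outcome being measured.

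The original-window summary does not repair this. Only the reset summary is limited to data after escalation. A subject who escalates at Month 20 enters the original Month 6 and Month 18 windows with results obtained on 5 mg before the flare. What is at stake is the endoscopic part of the answer to a named secondary objective.

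**Working it through.** The plan gives no figure for endoscopy coverage after escalation. Its one design figure, a 95% half width of about 16% at Month 6, reproduces as 1.96 × √(2 × 0.7 × 0.3 / 65) = 15.75%, but does not bear on this point.

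**Inputs.** Scheduled endoscopies at Days 180, 540, 900 and 1260 and the reset windows (SAP Appendix 1 target days; Protocol Schedule of Activities); no escalation for flare before Month 1, about Day 30 (Protocol 5.11). The timing of escalation is not in the documents, so it is assumed over a range.

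**Step 1: position.** With escalation on study day D, an endoscopy on study day S falls on reset day S − D + 1. SAP 5.2 calls the escalation day Day 0 and Appendix 1 calls it Day 1; the one-day shift changes nothing below.

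**Step 2: simple geometry.** Scheduled endoscopies are 360 days apart. A 90-day window catches one for 90/360 = 25% of subjects; the Month 3 window catches one for 134/360 = 37%.

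**Step 3: coverage by escalation pattern.** Percentage with a scheduled endoscopy in the window, among subjects whose planned follow-up reaches it:

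| Assumed escalation | M3 | M6 | M9 | M12 | M15 | M18 | M21 | M24 |
|---|---|---|---|---|---|---|---|---|
| Uniform, Days 30-1260 | 43 | 26 | 27 | 29 | 32 | 26 | 28 | 32 |
| Uniform, Days 30-540 | 52 | 21 | 18 | 26 | 35 | 21 | 18 | 26 |
| Exponential, median 6 months | 50 | 19 | 18 | 26 | 38 | 19 | 19 | 28 |
| Exponential, median 24 months | 44 | 24 | 24 | 28 | 33 | 24 | 25 | 30 |
| Equal across visits | 29 | 31 | 25 | 27 | 30 | 33 | 25 | 28 |
| 30% at Month 6/18/30 endoscopies, rest uniform | 30 | 18 | 18 | 55 | 21 | 17 | 17 | 61 |
| 80% at those endoscopies, rest uniform | 9 | 5 | 5 | 89 | 6 | 4 | 4 | 92 |

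One cell by hand (first row, Month 6): escalation on Days 30-45, 316-405, 676-765 or 1036-1125 puts a scheduled endoscopy in Days 136-225. That is 16 + 90 + 90 + 90 = 286 of the 1,096 days (30-1125) from which follow-up reaches the window, or 26%.

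**Step 4: escalation at a scheduled endoscopy.** The next one falls on Day 540 − 180 + 1 = 361 (Month 12 window, Days 316-405); after escalation at Month 6 or 18 the one after that falls on Day 900 − 180 + 1 = 721 (Month 24 window, Days 676-765). With ±7 days on each visit, Day 361 ranges over 347-375, still inside. For these subjects every endoscopy in the Month 3, 6 and 9 windows is unscheduled or ET.

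**Step 5: pull downward (illustration).** Assume true remission of 50%, 25% scheduled coverage, and a fraction f of the remaining failing subjects scoped for symptoms or at ET. The observed rate is 0.125 / (0.25 + 0.375f):

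- f = 0.1: 0.125/0.2875 = 43%; unscheduled or ET share of endoscopies 0.0375/0.2875 = 13%
- f = 0.3: 0.125/0.3625 = 34%; share 0.1125/0.3625 = 31%
- f = 0.5: 0.125/0.4375 = 29%; share 0.1875/0.4375 = 43%

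**Step 6: pull upward (illustration).** Suppose 20% of the subgroup are non-responders who left before the window. The observed rate is 0.125 / (0.20 + 0.225f), still against 50% of all escalated subjects:

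- f = 0.1: 0.125/0.2225 = 56%
- f = 0.3: 0.125/0.2675 = 47%

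The sign changes at f = 0.05/0.225 = 22%.

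**Step 7: endpoints without endoscopy.** Partial and modified partial Mayo subscores are collected at every scheduled visit. For escalation by Day 540, a scheduled visit falls in every reset window (100%).

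**The case against.** The case for leaving the plan alone has substance. No hypotheses are tested (SAP 5.1), this objective is descriptive, and the absence of imputation is stated openly. Number and proportion of responders are both reported (SAP 5.2.1), so small denominators will be visible. Partial and modified partial Mayo remission are already planned and fall within the reset summary. If flares are mostly confirmed at scheduled endoscopies, Months 12 and 24 are well covered. In the original windows, a subject who escalated by Month 6 has scheduled endoscopies on 10 mg at Months 18, 30 and 42, and showing earlier visits can be defended as a description of the whole course.

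All of this limits the reach of the point. It does not remove it. A visible denominator does not tell the reader why each subject was scoped, so the selection cannot be undone from the table. The clustering that helps Months 12 and 24 empties Months 3, 6 and 9 of scheduled endoscopies. The original-window table does not separate results on 5 mg from results on 10 mg.

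There is also a fair objection to the obvious remedy. Reporting only the first scheduled endoscopy, with ET results set aside, would drop early failures and inflate recovery. The fix has to keep those subjects in the denominator.

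**Conclusion.** The mismatch is real, and the endoscopic proportions in the reset windows are selected on outcome. With spread-out escalation, about 18-38% of subjects have a scheduled endoscopy in each Month 6-24 window and about 29-52% in Month 3. With escalation at a scheduled endoscopy, Months 3, 6 and 9 have none, while Months 12 and 24 are well covered (55-89% and 61-92% if 30-80% of escalations cluster there). These figures rest on assumed escalation timing and ignore missed visits; telephone visits under Protocol Appendix 9 would lower them.

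Two stronger readings are tempting, and the documents do not support either. A reader might infer that symptom-driven and ET endoscopies dominate these summaries. At 25% coverage that needs more than 0.25/0.75 = 33% of the other subjects to be scoped within one 90-day window. At 12% coverage (Months 6 and 9 with half of escalations clustered) it needs about 0.12/0.88 = 14%. No such rate is given. A reader might also infer that recovery is understated. That is likely among subjects still on study, but withdrawal of failures works the other way, and Step 6 shows the sign can reverse.

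Partial and modified partial Mayo remission are free of the endoscopy problem. The primary and regimen comparisons are unaffected.

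**What to change.** Amend SAP 5.2 and Appendix 1 for the re-treated subgroup:

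1. Flag each endoscopy after escalation as scheduled, symptom-driven or ET, and show counts and responders per window by reason.
2. Report endoscopic endpoints at the first scheduled endoscopy after escalation, grouped by time since escalation. Use all escalated subjects due for that endoscopy as the denominator. Count those who left earlier for lack of efficacy or new UC therapy as non-responders, and show other leavers separately.
3. Make partial and modified partial Mayo remission the main 3-monthly course in the reset windows, with the number of escalated subjects still due shown beside the number observed.
4. Limit the original-window efficacy summary to visits after escalation, or show results before and after escalation separately.
5. Use one day number for escalation in SAP 5.2 and Appendix 1.

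The cost is SAP wording and one derived flag, with no new procedure or visit. The price is fewer endoscopic time points, and time since escalation at the first scheduled endoscopy will range from days to about a year, which is why item 2 groups by it.

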5.2.1. Analyses for Binary Efficacy Data

The number and proportion of responders will be presented by dose group, regimen group and the subgroup of subjects who are initially assigned to tofacitinib 5 mg BID and later are retreated with tofacitinib 10 mg BID as described in [Section 5.2](#).

For dose comparison between tofacitinib 10 mg BID and 5 mg BID, the stratified estimation of the treatment difference between tofacitinib 10 mg BID and 5 mg BID in the proportion of subjects will be presented along with its 95% confidence interval (CI) with the endoscopic

subscore at baseline (0 versus 1) as the stratification factor. The Cochran Mantel Haenszel (CMH) weight method will be used for the stratified estimation of the treatment difference. The stratified CI will be constructed using the NewCombe method by Yan and Su (2010).¹ In addition, p-value based on CMH Chi-square test stratified by endoscopic subscore at baseline (0 versus 1) will be presented. The same analysis method will be used for regimen groups.

For the second secondary objective, in the subgroup of subjects who are initially assigned to tofacitinib 5 mg BID and later are retreated with tofacitinib 10 mg BID, the number and proportion of responders will be also presented overall and by the endoscopic subscore at baseline (0 versus 1).

As sensitivity analyses for handling of missing data, remission based on modified Mayo score and remission based on total Mayo score will also be analyzed using a generalized linear mixed-effects model with a logit link and with dose group, visit, dose group by visit interaction, endoscopic subscore at baseline (0 versus 1) all as fixed effects, and subject as a random effect based on data collected at Month 6, Month 18, Month 30 and Month 42 if sufficient data are available at Month 42. The estimated mean, mean difference, with p-values and 95% confidence interval based on the model will be presented at each time point for dose group and regimen group.

